1. INTRODUCTION

This document describes the rules and conventions to be used in the presentation, summarizing and analysis of data from participants receiving belantamab mafodotin (GSK2857916) in another GSK trial or patients on commercial prescriptions. This is an exploratory study, and only descriptive statistics apply.

This statistical analysis plan (SAP) is based on protocol 214098 amendment 02 (TMF-11824254), dated 04 February 2021.

2. STUDY OBJECTIVES

2.1. PRIMARY OBJECTIVE

[figure not shown]
The primary objective is to characterize corneal epitheliopathy in participants treated with belantamab mafodotin.

2.2. SECONDARY OBJECTIVES

The secondary objectives are:

- To correlate clinical data, including visual acuity and symptoms, as well as grade and appearance of corneal changes on imaging, with histopathologic findings.
- To describe safety profile of the impression cytology (IC) or superficial keratectomy (SK) procedure.

CCI

Document: \\ieedc-vnasc01\Biosdata\GSK\GSK2857916\UZA78766\Biostatistics\Documentation\SAP\UZA78766_214098_SAP_v2.0_12OCT2022.docx

Author: PPD

Version Number: 2.0

Version Date: 12OCT2022

Template No.: CS_TP_BS016 Revision 6

Reference: CS_WI_BS005

Effective Date: 02Dec2019

3. STUDY DESIGN

3.1. GENERAL DESCRIPTION

- This study is available to any participant who has received or is currently receiving belantamab mafodotin treatment through a clinical trial (including an investigator- sponsored study (ISS), or an access program) or a Physician prescription; they do not need to be on active treatment as long as they meet inclusion criteria (See protocol amendment 02 (TMF-11824254) – Section 5 STUDY POPULATION).
- Up to 25 participants will complete the procedure. Once a total of 5 participant samples from SK procedure has yielded evaluable material for pathologic examination and composition analysis of the corneal epithelial changes, further enrollment will cease.
- Each patient will have a total of 3 (IC) to 6 (SK) visits. Additional follow-up visits may be required in the event of delay in healing from the ocular procedures.
- One eye will be the study eye. The study eye will be the eye most affected with the corneal epithelial changes. If both eyes are equally affected, the poorer-seeing eye will be selected.
- **CCI**

Impression cytology: Following topical anesthesia, an eyelid speculum, will be placed. Next, the filter paper will be pressed to a preidentified region on the corneal surface of the study eye with a glass rod (or similar instrument) for 5–10 seconds. The filter papers obtained from the procedure will contain epithelial layers from areas of the cornea with microcyst-like changes and will be analyzed through histologic techniques.
- **Superficial keratectomy:** Following topical anesthesia (such as proparacaine hydrochloride 0.5%) and a drop of povidone iodine 5% for antisepsis, an eyelid speculum will be placed. The eye will then be visualized using a slit-lamp or operating microscope in a procedure room. The corneal epithelium of interest (the region that contains the MECs) will be carefully removed using either a Weck-Cel/dry cellulose sponge or small blade; Jeweler or 0.12 forceps may be required in some cases. The tissue will be submitted in formalin for histologic analysis.
- **Study Duration:** approximately 4 weeks.

Document: \\ieedc-vnasc01\Biosdata\GSK\GSK2857916\UZA78766\Biostatistics\Documentation\SAP\UZA78766_214098_SAP_v2.0_12OCT2022.docx

Author: PPD

Version Number: 2.0

[figure not shown]
Version Date: 12OCT2022

Template No.: CS_TP_BS016 Revision 6

Reference: CS_WI_BS005

Effective Date: 02Dec2019

Table A: Study schema

Document: \\ieedc-vnasc01\Biosdata\GSKGSK2857916\UZA78766\Biostatistics\Documentation\SAP\UZA78766_214098_SAP_v2.0_12OCT2022.docx

Author: PPD

Version Number: 2.0

Version Date: 12OCT2022

Template No.: CS_TP_BS016 Revision 6

Reference: CS_WI_BS005

Effective Date: 02Dec2019

3.2. SCHEDULE OF ACTIVITIES

Procedure	Screening	Pre-IC or SK procedure	IC or SK procedure (day of procedure)	Post-IC or SK procedure*	Safety follow-up (up to 1 week after SK procedure)	Safety follow-up (2 weeks after SK procedure) ^t	Additional follow-up at ophthalmologist's discretion ^s
Informed consent	X						
Eligibility criteria	X						
Slit-lamp examination and confocal microscopy (if available) ^a with imaging		X			X ^d		
Snellen eye test ^a			X		X	X	
CCI							
Corneal tissue sampling ^c			X				
Pathology review of corneal sample				X			
Ophthalmology post-procedure checkup							X
Vital signs (pulse and blood pressure)			X				
AEs/SAEs			X	X	X	X	
Data Collection ^b	X	X	X	X	X	X	X
CCI							

AE, adverse event; CCI

IC, impression cytology; SAE, serious adverse event; SK, superficial keratectomy.

Document: \\ieedc-vnasc01\Biosdata\GSK\GSK2857916\UZA78766\Biostatistics\Documentation\SAP\UZA78766_2140
 98 SAP v2.0 12OCT2022.docx
 PPD

Author:

Version Number: 2.0

Version Date: 12OCT2022

Template No.: CS_TP_BS016 Revision 6

Reference: CS_WI_BS005

Effective Date: 02Dec2019

^a An ophthalmic examination that includes best-corrected visual acuity, slit-lamp examination, and confocal microscopy (if available) must be performed prior to the impression cytology or keratectomy procedure to document site and size of corneal epithelial changes and to correlate imaging with pathologic findings. The slit lamp examination must include orbit/lid/adnexa, conjunctiva, sclera, cornea, anterior chamber, iris, lens, and anterior vitreous. Confirmatory anterior segment photography is also required unless acceptable corneal images are available from an examination performed <14 days prior to impression cytology or SK. It is recommended that the imaging examination be performed at least 24 hrs prior to the procedure.

^b Examples of preferred terms (CTCAE v5.0) include, but are not limited to, keratitis, eye disorder–other, blurred vision, dry eye, eye pain, flashing lights, photophobia, and watering eyes.

^c GSK may store samples for up to 3 years after the end of the study to achieve study objectives. Additionally, with participants' consent, samples may be used for further research by GSK or others such as universities or other companies to contribute to the understanding of the pathophysiology of belantamab mafodotin – associated keratopathy, the development of related or new treatments, or research methods.

^d Preferred timing for follow-up slit-lamp examination is 24–48 hours post SK procedure but must be performed within 1 week after SK procedure. Safety follow-up after impression cytology is not required unless the participant is experiencing discomfort or an AE.

^e The AE/SAE follow-up immediately after the Post-IC or SK procedure can be done by phone, in the 24–48 hours post-procedure.

^f The participant should be reexamined 2 weeks after the SK procedure if the epithelial defect does not heal completely in the first follow-up. Otherwise, this follow-up is not required.

^g In the event the cornea has not healed at 2 weeks, additional follow-up should be conducted at the ophthalmologist's discretion until healing is confirmed.

^h Minimal additional data will be collected to adequately characterize the development of the corneal epithelial changes in participating patients.

CCI

Document: \\ieedc-vnasc01\Biosdata\GSK\GSK2857916\UZA78766\Biostatistics\Documentation\SAP\UZA78766_214098_SAP_v2.0_12OCT2022.docx

Author: PPD

Version Number: 2.0

Version Date: 12OCT2022

Reference: CS_WI_BS005

[figure not shown]
Template No.: CS_TP_BS016 Revision 6

Effective Date: 02Dec2019

3.3. CHANGES TO ANALYSIS FROM PROTOCOL

Impression cytology or superficial keratectomy procedure population (ICSK) and evaluable impression cytology or superficial keratectomy procedure population (EICSK) are not defined in the protocol amendment 02 (TMF-11824254) but have been added since an enrolled participant may not undergo either impression cytology or superficial keratectomy. These populations have been defined in Section 5.3.

CCI

4. PLANNED ANALYSES

An interim analysis will be performed only if the 5 SK patients target is not met by the planned Final Analysis timeline – final analysis would then be completed once the final recruitment is achieved. If the 5 SK patients target is met by the planned Final Analysis delivery time, then no interim analysis will be performed, and only final analysis will be performed.

Data monitoring committee analyses are not planned.

4.1. FINAL ANALYSIS

The end of the study is defined as the date of the last visit of the last participant in the study or last scheduled procedure shown in the schedule of activities (Section 3.2) for the last participant in the trial.

A participant is considered to have completed the study if he/she has completed all phases of the study including the

Document: \\ieedc-vnasc01\Biosdata\GSKGSK2857916\UZA78766\Biostatistics\Documentation\SAP\UZA78766_214098_SAP_v2.0_12OCT2022.docx

Author: PPD

Version Number: 2.0

Version Date: 12OCT2022

Template No.: CS_TP_BS016 Revision 6

Reference: CS_WI_BS005

Effective Date: 02Dec2019

last visit, as specified in the schedule of activities (Section 3.2).

All final, planned analyses identified in this SAP will be performed by IQVIA Biostatistics following Sponsor Authorization of this statistical analysis plan, output templates and database lock.

5. ANALYSIS POPULATIONS

5.1. ALL PARTICIPANTS SCREENED

All participants screened population will contain all participants who signed informed consent.

5.2. ALL-TREATED POPULATION

All-treated population is defined as all participants screened who are enrolled (without screen failure).

5.3. IMPRESSION CYTOLOGY OR SUPERFICIAL KERATECTOMY PROCEDURE (ICSK) POPULATION

IC or SK (ICSK) population is defined as participants from all-treated population who had a tissue sample collected using Impression Cytology (IC) or Superficial Keratectomy (SK) procedure, whether or not the specimen is evaluable.

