6. STUDY INTERVENTION(S) AND CONCOMITANT THERAPY

6.1. Study Intervention(s) Administered

Impression cytology is a technique used to collect superficial layers from the ocular surface through the application of cellulose acetate filter paper. The procedure is performed with or without topical anesthesia by an ophthalmologist or ocular pathologist.

SK is a method to remove a small region of the corneal epithelium down to but not including the level of the Bowman's membrane. This procedure will be performed by an ophthalmologist and will be conducted in the eye clinic or hospital under local anesthesia with appropriate antisepsis.

In this study, impression cytology or SK will be employed to collect corneal epithelium with epithelial changes for analysis.

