6.3. Impression Cytology Procedure

The study eye will be selected using the criteria described above. Following topical anesthesia, an eyelid speculum, will be placed. Next, the filter paper will be pressed to a preidentified region on the corneal surface of the study eye with a glass rod (or similar instrument) for 5–10 seconds. The filter papers obtained from the procedure will contain epithelial layers from areas of the cornea with microcyst-like changes and will be analyzed through histologic techniques. The filter paper will be placed on a glass slide and cover slip placed on top. The eye speculum will be removed and a topical antibiotic drop (e.g. polytrim) will be prescribed for 4 times a day for 7 days.

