17.2. SECONDARY SAFETY ENDPOINTS

17.2.1. ADVERSE EVENTS

Adverse Events (AEs) related to the IC or SK procedure only will be collected from the start of intervention until the last follow-up visit at the time points specified in the schedule of activities (Section 3.2).

All Serious Adverse Events (SAEs) related to the IC or SK procedure only will be collected from the start of intervention until the last follow-up visit at the time points specified in the schedule of activities (Section 3.2). However, any SAEs assessed as related to study participation (e.g., study intervention, protocol-mandated procedures, invasive tests) will be recorded from the time a participant consents to participate in the study.

AEs and SAEs will be presented on the ICSK population and coded using MedDRA version 23.0 or above.

An overall summary table of number of participants within each of the categories described below, will be provided by method of tissue collection (impression cytology/superficial keratectomy) summarizing:

- Participants with at least one AE related to the IC or SK procedure.
- Participants with at least one SAE related to the study participation or to the IC or SK procedure.
- Participants with at least one SAE leading to study discontinuation
- Participants with AE leading to death.

AEs and SAEs will be presented in tables by PT and sorted by decreasing frequencies on total, and broken down by maximum grade. AEs will be graded according to the NCI Common Terminology Criteria of Adverse Events (NCI CTCAE) Version 5.0.

Participants will be counted only once for each PT even if they have multiple records of the same PT. If a participant reports an AE more than once within that PT, the AE with the worst-case grade will be used in the corresponding grade summaries.

Document: \\ieedc-vnasc01\Biosdata\GSKGSK2857916\UZA78766\Biostatistics\Documentation\SAP\UZA78766_214098_SAP_v2.0_12OCT2022.docx

Author: PPD Version Number: 2.0
Version Date: 12OCT2022

Template No.: CS_TP_BS016 Revision 6

Reference: CS_WI_BS005

Effective Date: 02Dec2019

AEs leading to Death are those events which are recorded on the Adverse Events page of the parent study eCRF as at least one of the following criteria:

- AE Term: "Death"
- Outcome: "Death related to adverse event"
- Seriousness: Results in death
- Toxicity grade (CTCAE): Grade 5

[figure not shown]
AEs leading to death will be presented in a by-participant listing on the all-treated population.

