All secondary safety data will also be included in a by-participant listing on the all-treated population.

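### The AE tables require a collected tissue sample, so an IC or SK that is started but yields no specimen drops out of their numerators and denominators (narrow case, low severity)

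*SAP*

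**What the plan says.** The table population is fixed by SAP 17.2.1: "AEs and SAEs will be presented on the ICSK population". SAP 5.3 defines that population as members of the all-treated population "who had a tissue sample collected using Impression Cytology (IC) or Superficial Keratectomy (SK) procedure, whether or not the specimen is evaluable". The only condition it waives is evaluability. A sample must still have been collected.

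The collection window is also in SAP 17.2.1. Procedure-related AEs are "collected from the start of intervention until the last follow-up visit at the time points specified in the schedule of activities". Neither document defines when the intervention starts. Both describe steps that precede sampling. For SK, SAP 3.1 has "Following topical anesthesia (such as proparacaine hydrochloride 0.5%) and a drop of povidone iodine 5% for antisepsis, an eyelid speculum will be placed" before any epithelium is touched. For IC, Protocol 6.3 has "Following topical anesthesia, an eyelid speculum, will be placed" before the filter paper is pressed.

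The listings are wider: "All secondary safety data will also be included in a by-participant listing on the all-treated population".

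Two rows of the SAP 17.2.1 overview table also matter. One counts participants with an SAE related to study participation or to the procedure, and the same section records participation-related SAEs from consent. The other counts participants with an SAE leading to study discontinuation. Protocol 9.3 says that nonserious AEs leading to discontinuation will be summarized as well.

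**The concern.** The safety profile of the procedure is a secondary objective, and its endpoint (Protocol 3) is AEs associated with the procedure, not with a specimen. Under SAP 5.3 and 17.2.1, whether a participant counts in the AE tables depends on how the procedure turned out. Someone who received drops and a speculum and then stopped is inside the AE collection window but outside the table. Attempts may stop for any reason, but those stopped because of an event are among the ones removed.

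The tables are split by method of tissue collection in a study of at most 25 participants, so one missing person can visibly change a column. Someone reading only the tables would not see that person.

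The participation-related SAE row has a similar problem that does not depend on how the start of the intervention is read. It covers events from consent onward, but only people with a collected sample can enter it. The discontinuation row is a separate matter: it is narrower than what Protocol 9.3 promises.

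**Working it through.** The plan states no figure to reproduce. The study is descriptive, and neither the target of 5 evaluable SK samples nor the ceiling of 25 participants comes from a calculation. The check is a trace of definitions, followed by an illustration.

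**Trace for the main point**

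1. Entry to the AE tables: a tissue sample was collected (SAP 5.3 through 17.2.1).
2. Entry to the AE collection window: the intervention has started (SAP 17.2.1, Protocol 8.1.3). Day 1 is the day of the procedure (SAP 6.1), not the date of a sample.
3. Steps before any sample: anesthesia, povidone iodine and speculum for SK (SAP 3.1); anesthesia and speculum for IC (Protocol 6.3).
4. A participant who stops during step 3 meets condition 2 but not condition 1.
5. SAP 3.3 adds ICSK because some enrolled participants may undergo neither procedure. That reason covers people in whom nothing was started. It does not address people in whom something was.

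**Trace for the two rows**

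- Participation-related SAEs are recorded from consent. Study activities precede sampling: the corneal sensation check at screening (Protocol 6.2.2), slit-lamp examination with fluorescein (Protocol 6.9) and the sBCMA blood sample (Protocol 6.8). The all-treated population (SAP 5.2) omits screen failures. Only the all-screened population (SAP 5.1), which is everyone who signed consent, matches the recording window.
- Protocol 9.3 covers nonserious AEs leading to discontinuation. The SAP row covers SAEs only.

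**Illustration**

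Let n participants have a sample, k of them with an event, and let m attempts give no specimen, j of them with an event. The planned table shows k/n. A procedure-started table shows (k + j)/(n + m). The planned figure is lower when j/m exceeds k/n and higher when j/m is below it.

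Assumptions: m = 1, and the event counts shown. The values 5 and 25 are the SK target and the study ceiling. The column with 3 sampled out of 4 started is an assumed shortfall. SAP 4 allows for one: "An interim analysis will be performed only if the 5 SK patients target is not met by the planned Final Analysis timeline".

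| Case | Planned table, k/n | Procedure started, (k + j)/(n + m) |
|---|---|---|
| Event only in the no-specimen attempt (k = 0, j = 1) | 0/3 = 0% | 1/4 = 25.0% |
| same | 0/5 = 0% | 1/6 = 16.7% |
| same | 0/24 = 0% | 1/25 = 4.0% |
| Event only in one sampled participant (k = 1, j = 0) | 1/3 = 33.3% | 1/4 = 25.0% |
| same | 1/5 = 20.0% | 1/6 = 16.7% |
| same | 1/24 = 4.2% | 1/25 = 4.0% |

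In the last three rows the planned table is higher by 8.3, 3.3 and 0.2 points. With m = 0 the two columns are identical.

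**The case against.** The strongest case is that the gap is close to empty. Every collected specimen stays in ICSK even if it cannot be read, and a filter paper that has been pressed would normally count as collected. What remains is a procedure abandoned after drops or speculum, or lost tissue, and the documents give no sign of how often that happens. With at most 25 participants and no tests, the all-treated listing is a main safety output, and the event is in it. Adding partial attempts can also dilute the rate, as the lower half of the table shows.

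The percentages deserve little weight. Each assumes one aborted attempt and a chosen pattern of events. Protocol 2.2 describes discomfort after SK as common, so an SK column otherwise free of events is an unlikely baseline. The SK column may exceed 5, because ICSK includes non-evaluable specimens. The pairs with 24 and 25 describe all participants together, not a typical single-method column.

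A reader might infer that the SAP contradicts Protocol 9.3, which puts everyone who has SK into the safety analysis, or departs silently from Protocol 9.1, which bases all analyses on enrolled participants. The documents do not support either reading. Protocol 6.1 says "SK is a method to remove a small region of the corneal epithelium", so an attempt that removed nothing can be read as not having been SK. SAP 3.3 openly declares the added populations as a change from the protocol. Nor are events concealed or lost.

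On the discontinuation row, nonserious AEs are already tabulated by preferred term and maximum grade, so only the discontinuation flag is missing. The output templates are not among the documents and the disposition text is partly redacted. The point is therefore limited to the rows listed in SAP 17.2.1.

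These objections settle the size of the point but do not remove it. A listing does not correct a table's denominator, and the reason given in SAP 3.3 does not require a sample condition.

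**Conclusion.** The main point holds on the operative wording: a started procedure without a specimen is outside the AE table numerators and denominators. It is a low-severity matter, worth correcting because the correction is cheap. It rests on taking SAP 5.3 literally and on counting the preparatory steps as part of the intervention, which the documents leave undefined. Its numerical size is unknown. It is zero if no such attempt occurs and can go in either direction if one does.

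The two row-level points hold separately and do not depend on that reading. The participation-related SAE row sits on a set narrower than its recording window, and the discontinuation row is narrower than Protocol 9.3.

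**What to change.** **AE and SAE tables.** In SAP 17.2.1, base them on all enrolled participants in whom IC or SK was started, grouped by the procedure started, whether or not tissue was obtained. Define the start as the first study-procedure step in the study eye. That wording also works when IC is done without anesthesia, which Protocol 6.1 allows. Show the number with no tissue obtained in each column, so that any dilution is visible. Keep ICSK and EICSK for the tissue and clinical tables, and record the change in SAP 3.3.

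**Participation-related SAEs.** Show this row on the all-participants-screened population, with a further column like the one SAP 9 uses for participants with no tissue collected. Label the columns so that nobody is counted twice. Moving the row only to all-treated would still omit consented screen failures.

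**Discontinuation.** Make the row count all AEs leading to study discontinuation, split into serious and nonserious.

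**Cost.** One population definition, one definition of start, and small edits to the overview table and its template. No visits or assessments are added. One check comes first: the SAP mentions only the method of tissue collection (SAP 16) and a category for tissue not collected (SAP 9). It must be confirmed that the eCRF or source records identify the procedure started. If they do not, that item has to be obtained for the few participants without a specimen.

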5.4. EVALUABLE IMPRESSION CYTOLOGY OR SUPERFICIAL KERATECTOMY PROCEDURE (EICSK) POPULATION

Evaluable IC or SK (EICSK) population is defined as participants from all-treated population who had an evaluable tissue sample collected using IC or SK procedure. A tissue sample specimen will be determined to be evaluable by the pathologist in the pathology report.

Document: \\ieedc-vnasc01\Biosdata\GSK\GSK2857916\UZA78766\Biostatistics\Documentation\SAP\UZA78766_214098_SAP_v2.0_12OCT2022.docx

Author: PPD

Version Number: 2.0

[figure not shown]
Version Date: 12OCT2022

Template No.: CS_TP_BS016 Revision 6

Reference: CS_WI_BS005

Effective Date: 02Dec2019

CCI

